### 8.2.5 Objective response rate

The objective response rate is the proportion of all subject with confirmed PR or CR according to RECIST v.1.1, from the start of treatment until disease progression/recurrence (taking as

reference for progressive disease the smallest measurements recorded since the start of treatment).

### **8.2.6 Time to Progression**

A measurement from the date of randomization until the criteria for disease progression is met as defined by RECIST 1.1. Subjects who have not progressed or have died due to any cause will be right-censored at the date of the last disease evaluation or date of death.

### **8.2.7 Progression Free Survival**

A measurement from the date of randomization until the criteria for disease progression is met as defined by RECIST 1.1 or death occurs. Subjects who have not progressed will be right-censored at the date of the last disease evaluation.

### **8.2.8 Overall Survival**

Overall survival is defined by the date of randomization to date of death from any cause.

## **8.3 Measurement of Fatigue**

### **8.3.1 Multidimensional fatigue symptom inventory-short form (MFSI-SF)**

The MFSI-SF tool that was used in the original ginseng study by Barton et.al will be used in this clinical trial. Please see document entitled “Information about the Fatigue Symptom Inventory (FSI) and the Multidimensional Fatigue Symptom inventory (MFSI)” in the SPM for detailed information.

### **8.3.2 Patient –Reported Outcomes Measurement Information System (PROMIS)**

The Patient-Reported Outcomes Measurement Information System (PROMIS) initiative is an example of an effort to develop a standard battery of valid and reliable measures that can be used in symptom management and QOL research [5]. Please see the document entitled “PROMIS Fatigue Scoring Manual” in the SPM for detailed information.

## **9 DRUG INFORMATION**

The two drugs used in this trial are Regorafenib and Ginseng.

### **9.1 American Ginseng (*Panax quinquefolius*)**

Ginseng’s proposed mechanism based on preclinical and clinical data is by down regulating inflammatory pathways , decrease inflammation and modulate cortisol and the impact of chronic stress on the hypothalamic pituitary adrenal axis [7-12] .

### **Formulation**

Because ginseng is not regulated by the FDA and is a plant that is subject to all of the variables relevant to any agricultural crop, this study will use American Ginseng manufactured in Wisconsin, which was also used in the phase 3 clinical trial (Barton et al 2013) (Ginseng Board of Wisconsin, and Wausau, WI), and which is manufactured using good manufacturing practices by Beehive Botanicals (Hayward, WI).

## **Administration**

Subjects will take four 500-mg opaque capsules consisting of pure ground root of Wisconsin ginseng. Dosing will be twice a day at 1000 mg (around meal and at lunch or noon). Total dose is 2,000 mg per day.

## **Precautions**

Ginseng is known to interfere with blood coagulation and some components of ginseng can elevate plasma insulin levels, causing hypoglycemia. Treating physicians should closely monitor persons with hypoglycemia or those on anticoagulants per local standard of care.

## **Side Effects**

May cause insomnia, nervousness, restlessness, increased heart rate, increased blood pressure or nausea.

### **9.2 Regorafenib**

Regorafenib tablets will be packaged in high-density polyethylene bottles with a white child resistant closure and induction seal. Each bottle includes 30 tablets and a 3-gram desiccant. The bottles will have a label affixed containing study identification, product identification, and quantity of tablets. Once the drug has been received, it must be kept in a secure, dry location. Study drug must be stored in its original bottle at a temperature not above 25°C (77°F).

The study drug must be exclusively used for the investigation specified in this protocol and it will only be accessible to authorized staff.

## **Drug Logistics and Accountability**

All study drugs will be stored at the investigational site in accordance with Good Clinical Practice (GCP) and Good Manufacturing Practices (GMP) requirements and the instructions given by the clinical supplies department of the Institution and will be inaccessible to unauthorized personnel.

## **Storage and Handling**

Store all study drugs at 25°C (77°F); excursions are permitted from 15 to 30°C (59 to 86°F) [See USP Controlled Room Temperature].

Store study drugs in the original bottle.

Do not remove the desiccant from the original bottle. Keep the bottle tightly closed after first opening. Discard any unused tablets 28 days after opening the bottle.

## **Accountability**

The site investigator, or a responsible party designated by the site investigator, must maintain a careful record of the inventory and disposition of the agent (investigational or free of charge) using the NCI Drug Accountability Record or another comparable drug accountability form. (See the CTEP website at <http://ctep.cancer.gov/protocolDevelopment> for the "Policy and Guidelines for Accountability and Storage of Investigational Agents" or to obtain a copy of the drug accountability form.)

## **Destruction and Return**

At the end of the study, unused supplies of regorafenib and ginseng should be destroyed according to institutional policies. Destruction will be documented on the Drug Accountability Record Form. A certificate of destruction should be sent to HCRN (or designee).

## **Treatment compliance**

An adequate record of receipt, distribution, and return of all study drugs must be kept in the form of a Drug Accountability Form.

Subject compliance with the treatment and protocol includes willingness to comply with all aspects of the protocol, and to have blood collected for all safety evaluations. At the discretion of the site investigator, a subject may be discontinued from the trial for non-compliance with follow-up visits or study drug.

## **Adverse Events**

Site investigators should refer to the Safety Information section of the current IB or prescribing information for regorafenib, including the DCSI (development core safety information), for the expected side effects of regorafenib. As with any agent, there is always the potential for unexpected AEs, including hypersensitivity reactions. The IB will be updated if any new relevant safety data are obtained.

Therapeutic monitoring should be performed following dose selection or modification of regorafenib in a manner consistent with the local clinical standard of care. In general, subjects should be closely monitored for side effects of all concomitant medications regardless of the path of drug elimination.

## **10 ADVERSE EVENTS**

The descriptions and grading scales found in the NCI CTCAE v4 will be utilized for AE assessment. A copy of the CTCAE v4 can be downloaded from the CTEP website at <http://ctep.cancer.gov>. All forms for AE/SAE recording and reporting can be found in the Study Procedure Manual or in OnCore (Documents and Information Tab).

### **10.1 Definitions**

#### **10.1.1 Adverse Event (AE)**

In a clinical study, an AE is any untoward medical occurrence (i.e. any unfavorable and unintended sign [including abnormal laboratory findings], symptom, or disease) in a subject after providing written informed consent for participation in the study. Therefore, an AE may or may not be temporally or causally associated with the use of a medicinal (investigational) product. An adverse event may include the following: an adverse event occurring in the course of the use of a drug in professional practice; an adverse event occurring from drug overdose whether accidental or intentional; an adverse event occurring from drug withdrawal and any failure of expected pharmacological action.

### **10.1.2 Serious Adverse Event (SAE)**

An SAE is classified as any untoward medical occurrence that, at any dose, meets any of the following criteria:

- Results in death, other than death related to disease progression
- Is life-threatening.
  - The term ‘life-threatening’ in the definition refers to an event in which the subject was at risk of death at the time of the event; it does not refer to an event that hypothetically might have caused death if it were more severe.
- Requires inpatient hospitalization or prolongation of existing hospitalization.
  - A hospitalization or prolongation of hospitalization will not be regarded as an SAE if at least one of the following exceptions is met:
    - The admission results in a hospital stay of less than 24 hours.
    - The admission is pre-planned.  
(i.e. elective or scheduled surgery arranged prior to the start of the study)
    - The admission is not associated with an AE (e.g. social hospitalization for purposes of respite care).
    - However, it should be noted that invasive treatment during any hospitalization may fulfill the criterion of ‘medically important’ and as such may be reportable as an SAE dependent on clinical judgment. In addition, where local regulatory authorities specifically require a more stringent definition, the local regulation takes precedence.
- Results in persistent or significant disability/incapacity.
  - Disability means a substantial disruption of a person’s ability to conduct normal life’s functions.
- Is a congenital anomaly/birth defect.
- Is another medically important serious event.
  - An event may be considered an important medical event when, based upon appropriate medical judgment, it may jeopardize the subject and may require medical or surgical intervention to prevent one of the outcomes listed in the definitions above.

### **10.1.3 Adverse Drug Reaction**

Adverse reaction means any adverse event for which there is a reasonable possibility that the drug caused the adverse event. For the purposes of IND safety reporting, ‘reasonable possibility’ means there is evidence to suggest a causal relationship between the drug and the adverse event. A suspected adverse reaction implies a lesser degree of certainty about causality than adverse reaction, which means any adverse event caused by a drug.

### **10.1.4 Serious Adverse Drug Reaction**

A serious adverse drug reaction is an event that meets any of the criteria for seriousness as previously defined and has a possible causal relationship to the study drugs.

## **10.2 Adverse Event Reporting**

### **10.2.1 Site Requirements for Recording Adverse Events**

Adverse events (AEs) will be recorded from the time of consent and for 30 days after the last dose of study drugs, regardless of whether or not the event(s) are considered related to the study drugs. The descriptions and grading scales found in the revised NCI Common Terminology

Criteria for Adverse Events (CTCAE) v4 will be utilized for AE reporting. A copy of the CTCAE v4 can be downloaded from the CTEP website at <http://ctep.cancer.gov>.

All AEs considered related to study drug will be followed until resolution, return to baseline, or deemed clinically insignificant, even if this occurs post-trial.

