### 5.1.1 Treatment Schedules

#### 5.1.1.1 Regorafenib

Regorafenib 160 mg PO once daily will be taken for 3 weeks on/1 week off for 2 cycles. Four 40-mg regorafenib tablets should be taken once a day with approximately 8 fluid ounces (240 mL) of water after a low-fat (<30% fat) meal. Some examples of a low-fat meal are:

- Two slices of white toast with 1 tablespoon of low-fat margarine and 1 tablespoon of jelly and 8 ounces (240 mL) of skim milk (approximately 319 calories and 8.2 g of fat).
- One cup of cereal (i.e. Special K), 8 ounces (240 mL) of skim milk, one piece of toast with jam (no butter or marmalade), apple juice, and one cup of coffee or tea (2 g fat, 17 g protein, 93 g of carbohydrate, 520 calories).

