### **5.2.1 Dose Modifications for Ginseng**

For subjects randomized to receive ginseng there are no dose delays or reductions. If regorafenib is held due to toxicity, the ginseng may continue if the toxicity is attributed to regorafenib only.

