7. The End of Treatment visit should occur 30 days after completion of Cycle 2 ( $\pm$  7 days). Subjects who stop treatment prior to completion of Cycle 2 should have the EOT 30 days after discontinuation of treatment. Subjects who have an ongoing  $\geq$  grade 2 or serious AE (SAE) at this visit will continue to be followed until the AE resolves to  $\leq$  Grade 1 or baseline, deemed clinically insignificant, and/or until a new anti-cancer treatment starts, whichever is earlier.
8. Follow up will occur in all subjects after completion of Cycle 2 every 3 months for 18 months. Follow up may be accomplished via clinic visit, phone call, or other avenues as appropriate.
9. Day -7 only ECOG performance status need be obtained.
10. Urinalysis should be done if proteinuria is suspected as per site investigator's discretion.

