## **7.3 End of Treatment: At least 30 days ( $\pm 7$ ) after the last dose of Cycle 2**

- Complete physical examination
- Vital signs including BP, weight and ECOG performance status
- Laboratory testing:
  - Complete Blood Count (CBC) with differential and platelet count??
  - Complete metabolic profile (CMP)
  - PT/INR and aPTT
- Adverse event and concomitant medication assessment
- Administer MFSI-SF and PROMIS questionnaires
- Pill count

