#### **10.2.2 Site Requirements for Reporting Serious Adverse Events to HCRN**

Site investigators and other site personnel must report any SAEs occurring from the time of informed consent to 30 days after the last dose of study drugs. This includes events both related and unrelated to the study drugs.

The definition of “related” being that there is a reasonable possibility the drug caused the adverse experience.

Unrelated	The Adverse Event is clearly not related to the study drug(s)
Unlikely	The Adverse Event is doubtfully related to the study drug (s)
Possible	The Adverse Event may be related to the study drug (s)
Probable	The Adverse Event is likely related to the study drug (s)
Definite	The Adverse Event is clearly related to the study drug (s)

The completed SAE Submission Form (see SPM) must be sent to HCRN **within 24 hours** of discovery of the event. The form may be sent to HCRN either electronically to [[contact]](mailto:[contact]) or by fax to [contact]. The site investigator is responsible for informing the IRB and/or the Regulatory Authority of the SAE as per local requirements.

The original copy of the SAE Submission Form and the fax confirmation sheet/email must be kept within the site study file.

Follow-up information should be submitted to HCRN either electronically to [[contact]](mailto:[contact]) or by fax to [contact], using a SAE Submission Form stating that this is a follow-up to the previously reported SAE and providing the follow-up number if appropriate. Each re-occurrence, complication, or progression of the original event should be reported as a follow-up to that event regardless of when it occurs. The follow-up information should describe whether the event has resolved or continues, if and how it was treated, and whether the subject continued or withdrew from study participation.

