### **The secondary objectives are as follows:**

(1) To assess the difference in adherence to regorafenib between the 2 groups. We will assess regorafenib adherence at three times, at the end of the 3rd week of each cycle. Since the recommended dose is once daily for 21 days, a measure of adherence would be the number of pills (out of 21) that each subject takes during each cycle. Using this measure for each subject, we will first compare groups using a 2-sample t-test for cycle 1, cycle 2 and then overall. Next, we will define subjects as being adherent based on having taken their pills on 17 (or more) days out of 21 (i.e. over 80% adherence). Using this definition of adherence, we will fit a 2x2 table comparing adherence rates between groups using a 1 degree of freedom Chi-square test. In addition, the statistician will compare mean daily doses using a t test and median daily doses by using Mann-Whitney test. Our hypothesis for these analyses is that Ginseng will reduce fatigue and thus lead to greater adherence to regorafenib in subjects who are in the Ginseng arm when compared to the no ginseng arm

(2) To assess the difference in toxicities between the two arms. Fisher exact tests will be used to assess the difference in toxicities between the two groups as well as the proportion of subjects

who experience grade 3 or higher toxicities of any kind according to the data safety monitoring plan described below.

(3) To assess the difference in retention between the two arms. As subjects can drop out of the study at various times, we will use Kaplan-Meier methods to estimate the retention distributions in each group and a log-rank test to assess the difference in distributions between the two groups.

(4) Response rate and overall survival are secondary objectives for the trial. Overall survival (OS) as an endpoint is defined in section 8.2.8 of the protocol. OS will be estimated using the Kaplan-Meier method and 90% confidence intervals derived as described in Brookmeyer and Crowley. The median will be provided along with the corresponding 95% CI. Additionally, the 25% and 75% percentiles for these endpoints will also be provided.

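### The adverse-event capture window ends a week later by schedule in the ginseng arm, and the Fisher toxicity tests do not allow for it

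*Combined protocol and SAP*

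**What the plan says.** **Capture.** Section 10.2.1: "Adverse events (AEs) will be recorded from the time of consent and for 30 days after the last dose of study drugs". Section 10.2.2 gives serious events the same end point: sites "must report any SAEs occurring from the time of informed consent to 30 days after the last dose of study drugs". Section 9 states that "The two drugs used in this trial are Regorafenib and Ginseng", so in the ginseng arm the last dose of study drugs is the later of the two.

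**Dosing.** Section 5.1.1.1: "Regorafenib 160 mg PO once daily will be taken for 3 weeks on/1 week off for 2 cycles". Section 5 has ginseng taken every day for 8 weeks, and gives controls none. (The synopsis's statistical paragraph has the word placebo in the control arm's name, but sections 5 and 9 and the schedule of events contain no placebo.) Section 5.2.1 adds: "If regorafenib is held due to toxicity, the ginseng may continue if the toxicity is attributed to regorafenib only". Section 5.2.2.1 lets the other study treatment go on when regorafenib alone is discontinued after more than two dose reductions.

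**Analysis.** Comparing toxicity between arms is secondary objective 2. Section 11: "Fisher exact tests will be used to assess the difference in toxicities between the two groups", and the same test is named for the proportion with any event of grade 3 or higher. No common cut-off and no adjustment for observation time is stated.

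**End of Treatment visit.** Section 7.3 and the column heading in section 7 count 30 days "after the last dose of Cycle 2". Footnote 7 of the schedule says "The End of Treatment visit should occur 30 days after completion of Cycle 2" and places the visit for early stoppers 30 days after treatment is discontinued.

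**The concern.** A Fisher test on the proportion with at least one event is a fair comparison only if subjects in both arms are watched for comparable time. Here the end of the watch depends on the last dose of any study drug, and one arm has a second drug that runs longer. The ginseng arm therefore has more time in which an event can be counted, even if ginseng adds no toxicity.

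The imbalance also depends on toxicity. When regorafenib is stopped for toxicity, a control subject's window starts to close at once, while a ginseng subject who stays on ginseng is followed as if nothing had stopped. Section 11 handles unequal time for retention, with Kaplan-Meier estimates and a log-rank test, but has nothing comparable for toxicity. The result is meant to inform a follow-up trial, so a built-in tilt against ginseng should be removed.

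**Working it through.** The plan gives no figure for observation time by arm, so there is no figure of its own to reproduce on this point. Days count from Cycle 1 Day 1 as day 1.

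**1. Scheduled windows**
- Last regorafenib dose: 28 + 21 = day 49. Control window closes: 49 + 30 = day 79.
- Last ginseng dose: day 56. Ginseng window closes: 56 + 30 = day 86.
- Gap: 7 days; 86/79 = 1.089, or 8.9% longer.

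**2. Regorafenib stopped early, ginseng continued to day 56**
- Stop on day 42: 42 + 30 = day 72 against day 86, a gap of 14 days.
- Stop on day 21: 21 + 30 = day 51 against day 86, a gap of 35 days; 86/51 = 1.69.

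**3. When the gap shrinks**
- Both drugs stop on the same day: no gap.
- Regorafenib is delayed so that its last dose falls on or after day 56: no gap against a ginseng subject with the same regorafenib course.
- A control whose regorafenib runs past day 56 is followed longer than an on-schedule ginseng subject: the gap reverses.

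**4. Effect on proportions for on-schedule completers.** Assume no true effect of ginseng and a constant event hazard. If p is the control proportion by day 79, the ginseng proportion is 1 − (1 − p)^(86/79). The last two columns are exact Fisher rejection rates at two-sided 0.05 with 60 and 30 subjects.

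| Control p | Ginseng | Excess (points) | Fisher rejection, equal windows | Fisher rejection, 79 vs 86 days |
|---|---|---|---|---|
| 10% | 10.8% | 0.8 | 3.1% | 3.0% |
| 30% | 32.2% | 2.2 | 3.7% | 4.0% |
| 50% | 53.0% | 3.0 | 4.4% | 5.1% |
| 70% | 73.0% | 3.0 | 3.7% | 4.7% |

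The values of p are assumptions. For scale, one control subject is 1/30 = 3.3 points.

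**5. Conditional illustration with early stops.** Suppose a share f of subjects stops regorafenib on day 21 and every ginseng subject continues to day 56. The control proportion becomes (1 − f)·p + f·[1 − (1 − p)^(51/79)].
- p = 30%, f = 10%: 32.2 − 29.1 = 3.1 points.
- p = 50%, f = 40%: 53.0 − 44.4 = 8.5 points (from unrounded values).

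The documents give neither f nor the share that continues ginseng.

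**6. End of Treatment visit, on-schedule completers, ±7 days**
- Anchored to the last dose of Cycle 2: days 72–86 (control) and 79–93 (ginseng).
- Anchored to completion of Cycle 2 (footnote 7): days 79–93 in both arms.

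**The case against.** **Section 10.2.1 is a recording rule for sites, not an analysis window, and 30 days after last exposure is a reasonable safety convention.** Both statements are true, and they are why the reporting rule should stay. But section 11 names no other set of events, so the Fisher tests as written compare whatever was recorded.

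**For completers the effect is small.** This stands. The excess is below one control subject, and the gap is no larger than the ±7-day tolerance of the End of Treatment visit. Section 1 reports that most regorafenib adverse events occurred in cycles 1–2, and days 79 to 86 fall 30 to 37 days after the last scheduled regorafenib dose, so a constant hazard probably overstates the effect.

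**Stronger readings that the documents do not support:**
- *A bias of up to about 9 points.* Step 5 reaches that size only with 40% stopping regorafenib on day 21 and every ginseng subject continuing to day 56. No stopping rate is given. Section 5.2.1 lets ginseng continue only when the toxicity is attributed to regorafenib alone, and footnotes to the hand-foot and hypertension tables take some subjects off protocol therapy.
- *Capture is always a week or more longer with ginseng.* The gap is exactly 7 days on schedule and can be zero or reversed (step 3). A ginseng subject who stops both drugs early also has an early cut-off.
- *The End of Treatment visit falls later in the ginseng arm.* That follows from section 7.3 and the column heading but not from footnote 7, which gives completers the same day in both arms. This is a contradiction in wording, not an established arm difference.

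**Conclusion.** The concern holds in a limited form. The plan builds in unequal capture time, 79 against 86 days by schedule, and tests raw proportions without allowing for it. The tilt is modest and runs against ginseng: about 1 to 3 percentage points for on-schedule completers, assuming a constant hazard and control event proportions of 10% to 70%, and less if events come early. Early regorafenib stops with ginseng continued would enlarge it, by an amount that cannot be determined from the documents.

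This does not invalidate the safety data, and at the scheduled gap it barely moves the false-positive rate. It is worth correcting because it arises from the design and depends on both arm and toxicity.

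**What to change.** **Comparison window.** Keep recording and reporting to 30 days after the last dose. In section 11, define the between-arm toxicity comparison as adverse events with onset within one window counted from Cycle 1 Day 1, the same in both arms and independent of when either drug stops. Day 79 is one choice and adds no follow-up for on-schedule completers. Continue adverse-event recording to that day for early stoppers in both arms. Report later events separately.

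**Sensitivity analysis.** Add a time-to-first-event comparison censored at the end of each subject's capture, or exposure-adjusted rates. Censoring is likely to be informative when the window closes because of toxicity, so this should support the common-window comparison and not replace it.

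**Cost.** Mainly wording, plus some added recording: a control subject who stops on day 21 needs 79 − 51 = 28 more days. Phone contact would miss laboratory toxicities. The added time may include events on later anticancer therapy, which should be flagged using the treatment start dates collected under section 7.4.

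**End of Treatment anchors.** Separately, reconcile the column heading in section 7, section 7.3 and footnote 7. They conflict on whether the visit counts from the last dose of Cycle 2 or from its completion. Footnote 7 also leaves open what discontinuation of treatment means when one drug stops and the other continues. No particular visit day is proposed here.
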